6.3 Laboratory Test Result Abnormalities

The following laboratory test result abnormalities should be captured on the non-serious AE CRF page or SAE Report Form (paper or electronic) as appropriate:

- Any laboratory test result that is clinically significant or meets the definition of an SAE.
- Any laboratory test result abnormality that required the subject to have study drug discontinued or interrupted.
- Any laboratory test result abnormality that required the subject to receive specific corrective therapy.

It is expected that wherever possible, the clinical rather than laboratory term would be used by the reporting investigator (eg, anemia versus low hemoglobin value).

6.4 Pregnancy

If, following initiation of the investigational product, it is subsequently discovered that a study subject is pregnant or may have been pregnant at the time of investigational product exposure, including during at least 5 half-lives + 30 days (165 days) after product administration, the investigational product will be permanently discontinued in an appropriate manner (eg, dose tapering if necessary for subject safety).

Protocol-required procedures for study discontinuation and follow-up must be performed on the subject unless contraindicated by pregnancy (eg, x-ray studies). Other appropriate pregnancy follow-up procedures should be considered if indicated.

The investigator must immediately notify the BMS (or designee) Medical Monitor of this event and complete and forward a Pregnancy Surveillance Form to BMS (or designee) within 24 hours and in accordance with SAE reporting procedures described in [Section 6.1.1](#).

Follow-up information regarding the course of the pregnancy, including perinatal and neonatal outcome and, where applicable, offspring information must be reported on the Pregnancy Surveillance Form.

Any pregnancy that occurs in a female partner of a male study participant should be reported to BMS. Information on this pregnancy will be collected on the Pregnancy Surveillance Form.

In cases where a study drug can be present in seminal fluid, at exposures sufficient to potentially cause fetal toxicity, and if any sexual activity (eg, vaginal, anal, oral) has occurred between a male participant and a pregnant WOCBP partner(s), the information should be reported to the Sponsor or designee, even if the male participant has undergone a successful vasectomy. In order for Sponsor or designee to collect any pregnancy surveillance information from the female partner, the female partner(s) must sign an informed consent form for disclosure of this information. Information on the pregnancy will be collected on the Pregnancy Surveillance Form.

6.5 Overdose

An overdose is defined as the accidental or intentional administration of any dose of a product that is considered both excessive and medically important. Overdose, as a verbatim term (as reported by the investigator), should not be reported as an AE/SAE unless it is an intentional overdose taken with possible suicidal/self-harming intent. Such overdoses should be reported regardless of sequelae and should specify "intentional overdose" as the verbatim term.

All occurrences of intentional overdose must be reported as an SAE (see [Section 6.1.1](#) for reporting details).

6.6 Potential Drug Induced Liver Injury (DILI)

Wherever possible, timely confirmation of initial liver-related laboratory abnormalities should occur prior to the reporting of a potential DILI event. All occurrences of potential DILIs, meeting the defined criteria, must be reported as SAEs (see [Section 6.1.1](#) for reporting details).

Potential drug induced liver injury is defined as:

- 1) Aminotransferase (ALT or AST) elevation > 3 times upper limit of normal (ULN)
AND
- 2) Total bilirubin > 2 times ULN, without initial findings of cholestasis (elevated serum alkaline phosphatase),
AND
- 3) No other immediately apparent possible causes of aminotransferase elevation and hyperbilirubinemia, including, but not limited to, viral hepatitis, pre-existing chronic or acute liver disease, or the administration of other drug(s) known to be hepatotoxic.

6.7 Other Safety Considerations

Any significant worsening noted during interim or final physical examinations, electrocardiogram, radiologic exams, any other potential safety assessment required or not required by protocol should also be recorded as a non-serious or serious AE, as appropriate, and reported accordingly.

7 DATA MONITORING COMMITTEE AND OTHER EXTERNAL COMMITTEES

Not applicable.

[figure not shown]
8 STATISTICAL CONSIDERATIONS

8.1 Sample Size Determination

8.1.1 *Parts A and C - Dose Escalation*

[figure not shown]
The sample size at each dose depends on observed toxicity and cannot be precisely determined. Part A will have █ to █ subjects in each cohort.

8.1.2 *Part B Cohort Expansion for Monotherapy*

8.1.3 *Part D Cohort Expansion for Combination Therapy*

The objective of this expansion in combination with nivolumab is, in addition to demonstrating adequate safety and tolerability, to evaluate a favorable risk/benefit assessed by signal seeking for anti-PD-1/PD-L1 progressed nivolumab HL, improvement in complete response (CR) rate for anti-PD-1/PD-L1 naive HL relative to PD-1 monotherapies, and improvement in objective response rate (ORR) for DLBCL relative to existing available therapies.

[figure not shown]
[figure not shown]

Table 8.1.3-1: Example of a Two-stage Design Characteristics

8.2 Populations for Analyses

- **All Enrolled Subjects:** All subjects who signed an informed consent form and were registered into the IVRS.
- **All Treated Subjects:** All subjects who received at least one dose of study medication. This is the primary population for safety and efficacy analyses.
- **Response-Evaluable Subjects:** All treated subjects with measurable disease at baseline and one of the following: 1) at least one post-baseline tumor assessment, 2) clinical progression, or 3) death (if death occurred within 135 days after last relatlimab dose).
- **Pharmacokinetic Subjects:** All subjects who received at least one dose of relatlimab or nivolumab and have evaluable plasma/serum concentration data.
- **Immunogenicity Subjects:** All treated subjects with relatlimab or nivolumab who have baseline and at least one post baseline immunogenicity assessment.
- **Biomarker Subjects:** All treated subjects with available biomarker data.

8.3 Endpoints

8.3.1 Primary Endpoint(s)

The primary endpoint of this Phase 1 study is safety as measured at the study level by the rate of AEs, SAEs, AEs leading to discontinuation, deaths, and laboratory abnormalities, assessed during treatment and for up to 135 days after the last treatment. All subjects who receive at least one dose of relatlimab alone or in combination with nivolumab will be analyzed for safety.

Co-primary endpoint in Part D is objective response rate (ORR) and duration of response (DOR) (see [Section 8.3.2.3](#) for details).

8.3.2 Secondary Endpoint(s)

8.3.2.1 Pharmacokinetics

The PK of relatlimab administered both alone and in combination with nivolumab will be assessed as a secondary objective using the following endpoints derived from serum concentration versus time data at time points indicated in [Table 5.5.1-1](#).

The PK parameters to be assessed include:

C _{max}	Maximum observed serum concentration
T _{max}	Time of maximum observed serum concentration
C _{trough}	Trough observed serum concentration
C _{tau}	Concentration at the end of a dosing interval (eg, concentration at 336 hours)
C _{ss,avg}	Average concentration over a dosing interval ($[AUC(TAU)]/\tau$)
AUC(TAU)	Area under the concentration-time curve in one dosing interval
CLT	Total body clearance
T-HALFeff AUC	Effective elimination half-life that explains the degree of AUC accumulation observed
T-HALFeff C _{max}	Effective elimination half-life that explains the degree of C _{max} accumulation observed
AI _{_AUC}	Accumulation index; ratio of AUC(TAU) at steady state to AUC(TAU) after the first dose
AI _{_Cmax}	C _{max} accumulation index; ratio of C _{max} at steady state to C _{max} after the first dose
AI _{_Ctau}	C _{tau} accumulation index; ratio of C _{tau} at steady state to C _{tau} after the first dose
DF	Degree of fluctuation or fluctuation index ($[C_{max} - C_{tau}]/C_{ss,avg}$)

Individual subject PK parameter values will be derived by noncompartmental methods by a validated PK analysis program. Actual times will be used for the analyses.

8.3.2.2 Immunogenicity

Incidence of ADA to either relatlimab or nivolumab will be assessed during treatment and for up to 135 days after their last treatment in post-treatment follow-up. Baseline ADA positive subject is defined as a subject with positive seroconversion detected in the last sample before initiation of treatment. ADA-positive subject is a subject with at least one ADA-positive sample relative to baseline after initiation of the treatment.

8.3.2.3 Efficacy

All efficacy analyses will be based on the all treated analysis population except otherwise stated. Co-primary, secondary and exploratory efficacy endpoints for Part D subjects are as follows:

Objective Response Rate (ORR)

ORR based on investigator assessment, according to the applicable criteria based on tumor type, will be co-primary endpoint in Part D. For the NHL and HL subjects, the ORR will be based on the IWG (2007) response criteria. In addition to the primary ORR endpoint, an exploratory endpoint of ORR based on the Lugano (2014) response criteria in the NHL and HL subjects in Part D will be assessed. For the Lugano criteria, response is defined as CMR and PMR.

Duration of Objective Response (DOR)

DOR is defined as the time between the date of first documented response (CR or PR) to the date of the first objectively documented progression as per criteria relevant to each disease type in Part D (Appendices 1, 2, and 6), or death due to any cause, whichever occurs first. For subjects who neither progress nor die, DOR will be censored on the date of their last tumor assessment. Subjects who start subsequent therapy without a prior reported progression will be censored at the last tumor assessments prior to initiation of the subsequent anticancer therapy. This endpoint will only be evaluated in subjects with objective response of CR or PR. DOR will be evaluated based on investigator assessments. DOR is a co-primary endpoint in Part D. DOR based on the Lugano (2014) response criteria, response defined as CMR or PMR, will be assessed for the NHL/HL subjects in Part D as an exploratory endpoint.

Complete Response (CR) Rate and Duration

The CR rate is defined as the number of subjects with a best overall response (BOR) of CR according to the applicable criteria based on tumor type, based on IWG criteria for NHL and HL subjects, divided by the number of treated subjects. The duration of CR (DoCR) will only be evaluated in subjects with BOR of CR and is defined as the time from first documentation of CR (the date of first negative FDG-PET scan) to the date of initial objectively documented progression as determined using the applicable criteria based on tumor type or death due to any cause, whichever occurs first. Censoring will be applied as per DOR definition. CR rate and DoCR will be evaluated based on investigator assessments. CR rate is an exploratory endpoint in this study.

Progression Free Survival (PFS) Rate

PFS is defined as the time from first dose to the date of first objectively documented progression, per applicable criteria based on tumor type or death due to any cause, whichever occurs first. Subjects who die without a reported progression will be considered to have progressed on the date of their death. Subjects who did not progress or die will be censored on the date of their last evaluable tumor assessment. Subjects who did not have any on study tumor assessments and did not die will be censored on the date of first dose. Subjects who started any subsequent anti-cancer therapy, including tumor-directed radiotherapy and tumor-directed surgery, without a prior reported progression will be censored at the last evaluable tumor assessment prior to initiation of the subsequent anti-cancer therapy. The PFS rate at time T is defined as the probability that a subject has not progressed and is alive at time T following first dose. PFSR will be assessed at Weeks 16, 24, 32, 40, and 100, and evaluated based on investigator assessments. PFS will be an exploratory endpoint in this study.

Overall Survival (OS) Rate

OS is defined as the time between the date of first dose and the date of death. For subjects without documentation of death, OS will be censored on the last date the subject was known to be alive. The overall survival rate at time T is defined as the probability that a subject is alive at time T following first dose OS will be assessed at various time points in HL patients in Part D.

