APPENDIX 1 2007 INTERNATIONAL WORKING GROUP (IWG) RESPONSE CRITERIA FOR MALIGNANT LYMPHOMA

2007 IWG Response Criteria for Malignant Lymphoma ¹				
Response	Definition	Nodal masses	Spleen, Liver	Bone marrow
CR	Disappearance of all evidence of disease	(a) FDG-avid or PET positive prior to therapy; residual mass of any size permitted if PET negative (b) Variably FDG-avid or PET negative; regression to normal size on CT	Not palpable, nodules disappeared	Infiltrate cleared on repeat biopsy; if indeterminate by morphology, immunohistochemistry should be negative
PR	Regression of measurable disease and no new sites	≥ 50% decrease in SPD of up to 6 largest dominant masses (index lesions); no increase in size of other nodes (non-index lesions) (a) FDG-avid or PET positive prior to therapy; one or more PET positive at previously involved site (b) Variably FDG-avid or PET negative; regression on CT	≥ 50% decrease in SPD of nodules (for single nodule in greatest transverse diameter); no increase in size of liver or spleen	Irrelevant if positive prior to therapy; cell type should be specified
SD	Failure to attain CR/PR or PD	(a) FDG-avid or PET positive prior to therapy; PET positive at prior sites of disease and no new sites on CT or PET (b) Variably FDG-avid or PET negative; no change in size of previous lesions on CT	N/A	N/A
Relapsed disease or PD	Any new lesion or increase by ≥ 50% of previously involved sites from nadir	Appearance of a new lesion(s) > 1.5 cm in any axis, ≥ 50% increase in SPD of more than one node (index lesions), or ≥ 50% increase in longest diameter of a previously identified node > 1 cm in short axis. Lesions PET positive if FDG-avid lymphoma or PET positive prior to therapy	> 50% increase from nadir in the SPD of any previous lesions	New or recurrent involvement

Key: CR = complete remission, CT = computed tomography; FDG = [18F] fluorodeoxyglucose; IWG = International Working Group; NA = Not applicable; PD = progressive disease; PET = positron-emission tomography; PR = partial remission; SD = stable disease; SPD = sum of the product of the diameters.

¹ Cheson, BD, Pfistner, B, Juweid, ME, et al. Revised criteria for malignant lymphoma. *J Clin Oncol.* 2007; 25:579.

CR (Complete Remission)

The designation of CR requires the following:

APPENDIX 1 Complete disappearance of all detectable clinical evidence of disease and disease-related symptoms, if present before therapy.

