APPENDIX 2 Typically [^{18}F] fluorodeoxyglucose (FDG)-avid lymphoma: in patients with no pretreatment positron emission tomography (PET) scan or when the PET scan was positive before therapy, a post-treatment residual mass of any size is permitted as long as it is PET negative.

APPENDIX 3 Variably FDG-avid lymphomas/FDG avidity unknown: in patients without a pretreatment PET scan, or if a pretreatment PET scan was negative, all lymph nodes and nodal masses must have regressed on computed tomography (CT) scan to normal size (≤ 1.5 cm in their greatest transverse diameter for nodes > 1.5 cm before therapy). Previously involved nodes that were 1.1 to 1.5 cm in their long axis and > 1.0 cm in their short axis before treatment must have decreased to ≤ 1.0 cm in their short axis after treatment.

APPENDIX 4 The spleen and/or liver, if considered enlarged before therapy on the basis of a physical examination or CT scan, should not be palpable on physical examination and should be considered normal size by imaging studies, and nodules related to lymphoma should disappear. However, determination of splenic involvement is not always reliable because a spleen considered normal in size may still contain lymphoma, whereas an enlarged spleen may reflect variations in anatomy, blood volume, the use of hematopoietic growth factors, or causes other than lymphoma.

APPENDIX 5 If the bone marrow was involved by lymphoma before treatment, the infiltrate must have cleared on repeat bone marrow biopsy. The biopsy sample on which this determination is made must be adequate (with a goal of > 20 mm unilateral core). If the sample is indeterminate by morphology, it should be negative by immunohistochemistry. A sample that is negative by immunohistochemistry but demonstrates a small population of clonal lymphocytes by flow cytometry will be considered a CR until data become available demonstrating a clear difference in patient outcome.

PR (Partial Remission)

The designation of PR requires all of the following:

1. At least a 50% decrease in the sum of the product of the diameters (SPD) of up to 6 of the largest dominant nodes or nodal masses. These nodes or masses should be selected according to all of the following: they should be clearly measurable in at least 2 perpendicular dimensions; if possible they should be from disparate regions of the body; and they should include mediastinal and retroperitoneal areas of disease whenever these sites are involved.

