2. No increase should be observed in the size of other nodes, liver, or spleen.
3. Splenic and hepatic nodules must regress by $\geq 50\%$ in their SPD or, for single nodules, in the greatest transverse diameter.
4. With the exception of splenic and hepatic nodules, involvement of other organs is usually assessable and no measurable disease should be present.
5. Bone marrow assessment is irrelevant for determination of a PR, if the sample was positive before treatment. However, if positive, the cell type should be specified (e.g., large-cell lymphoma or small neoplastic B cells). Patients who achieve a CR by the above criteria but have persistent morphologic bone marrow involvement will be considered partial responders. When the bone marrow was involved before therapy and a clinical CR was achieved but with no bone marrow assessment after treatment, patients should be considered partial responders.
6. No new sites of disease should be observed.
7. FDG:
 - a. Typically FDG-avid lymphoma: for patients with no pretreatment PET scan or if the PET scan was positive before therapy, the post-treatment PET should be positive in at least 1 previously involved site.
 - b. Variably FDG-avid lymphomas/FDG-avidity unknown: for patients without a pretreatment PET scan, or if a pretreatment PET scan was negative, CT criteria should be used. In patients with follicular lymphoma or mantle-cell lymphoma, a PET scan is only indicated with 1 or at most 2 residual masses that have regressed by $> 50\%$ on CT; those with more than 2 residual lesions are unlikely to be PET negative and should be considered partial responders.

SD (Stable Disease)

1. A patient is considered to have SD when he or she fails to attain the criteria needed for a CR or PR but does not fulfill those for progressive disease (see Relapsed Disease [after CR]/Progressive Disease [after PR, SD]).
2. Typically FDG-avid lymphomas: the PET should be positive at prior sites of disease with no new areas of involvement on the post-treatment CT or PET scan.
3. Variably FDG-avid lymphomas/FDG-avidity unknown: for patients without a pretreatment PET scan or if the pretreatment PET was negative, there must be no change in the size of the previous lesions on the post-treatment CT scan.

PD: Relapsed Disease (after CR)/Progressive Disease (after PR, SD)

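### Duration of complete response starts at the first negative FDG-PET, which can come before all the Appendix 1 criteria for CR are met

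*Combined protocol and SAP*

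**What the plan says.** In Section 8.3.2.3 (Complete Response Rate and Duration), DoCR is "defined as the time from first documentation of CR (the date of first negative FDG-PET scan) to the date of initial objectively documented progression", or to death if that comes first. The synopsis has the same definition, with the same start: "first documentation of CR (the date of first negative FDG-PET scan". DoCR "will only be evaluated in subjects with BOR of CR", and CR itself is "based on IWG criteria for NHL and HL subjects".

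Those criteria are in Appendix 1, which sets several conditions for CR:

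- **Clinical:** "Complete disappearance of all detectable clinical evidence of disease and disease-related symptoms, if present before therapy".
- **PET, in typically FDG-avid lymphoma:** "a post-treatment residual mass of any size is permitted as long as it is PET negative".
- **Spleen and liver:** if enlarged before therapy, they must be impalpable and of normal size on imaging, with lymphoma nodules gone.
- **Marrow:** "If the bone marrow was involved by lymphoma before treatment, the infiltrate must have cleared on repeat bone marrow biopsy".

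Item 5 of the PR definition covers the subject who is complete except for the marrow. Persistent morphologic involvement makes the response a PR. So does a missing reassessment of an involved marrow: where "a clinical CR was achieved but with no bone marrow assessment after treatment, patients should be considered partial responders".

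Section 8.3.3.3 uses the same PET parenthesis to start the duration of complete metabolic response (DoCMR) under Lugano 2014.

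**The concern.** The words before the parenthesis, taken alone, would be right. The parenthesis replaces a composite status with the date of one of its components. That suits DoCMR, because complete metabolic response is read from PET. It does not suit IWG CR, which can be completed later by a marrow biopsy, an organ examination or the loss of symptoms.

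Two uses of the result are at stake. Section 8.1.3 gives improvement in CR rate over PD-1 monotherapy as the aim for the anti-PD-1/PD-L1 naive Hodgkin cohort, so how long those CRs last is a natural companion result. The sponsor also wants to compare IWG 2007 with Lugano 2014. If DoCR and DoCMR both start at a PET date, part of any difference in when the two statuses are reached is lost.

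**Working it through.** The plan attaches no figure to DoCR, so there is nothing to reproduce. The check sets the start date against the criteria.

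**1. What a negative PET settles**

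| Appendix 1 element of CR | Applies when | Settled by the negative PET? |
|---|---|---|
| FDG-avid masses | typically FDG-avid disease | Yes |
| Symptoms and clinical evidence of disease | present before therapy | No |
| Spleen and liver size, palpation, nodules | enlarged before therapy | Not by PET alone |
| Marrow | involved before therapy | No, needs repeat biopsy |

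**2. Status on the PET date.** Take a subject with marrow involvement at baseline, a first negative PET on date t1, and the last outstanding element (here a clear marrow biopsy) on a later date t2. On t1 the involved marrow has not been reassessed, so PR item 5 makes the response a PR. On t2 it becomes a CR. Best overall response is CR, so the subject enters the DoCR analysis with t1 as the start.

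**3. Size for one subject.** Let T be the date of progression, death or censoring, which is the same under either start.

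- As written: DoCR = T − t1
- By Appendix 1: DoCR = T − t2
- Difference: (T − t1) − (T − t2) = t2 − t1 = L

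If every other element is already met by t1, the PET is itself the last element and L = 0. L is never negative, so the error runs one way. The lag is also event-free time. Nobody reaches CR after dying. Nobody reaches it after progressing either, provided best overall response counts only responses before progression. Section 8.3.2.3 does not spell that out, so it is an assumption here.

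**4. Size on average (illustration only).** If a share p of complete responders is affected, each with lag L, the mean overstatement of individual durations is p × L. The documents give neither p nor L. Assume p from 10% to 30%, and L of one or two cycles (Section 5.5.1: 56 days / 7 = 8 weeks per cycle).

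| Assumed L | p = 10% | p = 30% |
|---|---|---|
| 8 weeks | 0.10 × 8 = 0.8 weeks | 0.30 × 8 = 2.4 weeks |
| 16 weeks | 0.10 × 16 = 1.6 weeks | 0.30 × 16 = 4.8 weeks |

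If the marrow or other element follows the PET within days, the effect is close to zero. The shift in a Kaplan-Meier median would depend on which subjects are affected.

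**5. CR without PET.** Appendix 1 lets CR be judged on CT regression in variably FDG-avid or avidity-unknown disease, and on CT alone where PET is unavailable or not deemed necessary. Such a CR has no negative-PET date and so no DoCR start. Section 5.4 restricts the Lugano assessment to Part D subjects who had PET scans before and during treatment, which suggests that some may not have had them. The documents do not show whether any Part D CR would be assigned this way.

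**6. What does not move.** CR rate counts subjects with a best response of CR, whatever its date. ORR counts CR and PR together. DOR starts at the first CR or PR, so the label on t1 makes no difference to it.

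**The case against.** The best defence is that the parenthesis is a dating convention. Only subjects with an established IWG CR enter the analysis, so the phrase may simply name the scan that dates it. An imaging date also does not depend on when a biopsy happens to be booked. That is a coherent choice, but the plan does not state it as one. It says that CR is first documented on that date, and Appendix 1 can say otherwise.

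A second point is that PR item 7a expects a positive PET in at least one prior site for PR in typically FDG-avid lymphoma, so Appendix 1 is not tidy about a PET-negative PR. Item 5 nevertheless assigns PR explicitly in the marrow cases. Whatever the label on t1, CR is not complete until the last element is met.

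Third, the naive-Hodgkin aim concerns CR rate rather than its duration, CR rate is exploratory, and no hypothesis is formally tested. All of that stands and limits the importance.

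A reader might also infer more than the documents support:

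- **That DoCR is too long by about one 8-week interval per affected subject, and longer because marrow is repeated only when clinically indicated.** That marrow wording is in the consent items for a monotherapy escalation cohort and Part B (Section 3.3.1) and in the Part A and B marrow text (Section 5.7.7). The Part D marrow schedule is not visible in the public text.
- **That CT-based CRs in Part D certainly lack a start date.** Part D enrols Hodgkin lymphoma and DLBCL, and nothing places either in the variably avid group. The gap is conditional.
- **That all the dates needed are already collected.** The columns of the schedule tables are missing from the public text, so this cannot be confirmed.

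**Conclusion.** The point holds as a minor inconsistency in the definition. The start rule for DoCR does not match the criteria by which CR is judged. DoCR is overstated by the exact lag in complete responders whose last required element follows the first negative PET, and is unaffected in the rest. The affected group would be those with symptoms, spleen or liver enlargement, or marrow involvement at baseline. Its size and the lag are unknown, and the averages shown above rest wholly on assumed values. The missing start date matters only if a CR is assigned without PET. No conclusion about CR rate, ORR or the co-primary DOR depends on this.

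**What to change.** In Section 8.3.2.3 and the matching synopsis paragraph, replace the parenthesis with: *the first date on which all applicable Appendix 1 CR criteria are documented as met, ie, the date of the last required element*. The closing clause is needed because the elements may be assessed on different days. Keep the negative-PET date only for DoCMR, in Section 8.3.3.3 and its synopsis counterpart.

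The text change is one phrase in two places, and it also gives a CT-assigned CR a start date. Before adopting it, the sponsor should confirm that the case report form captures a date for each required element in Part D. The cost is that some reported CR durations become slightly shorter, and that the start date then depends on when the last required element was assessed.
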